#### **4.3 Exclusion criteria - amended**

- Concomitant use of the following medications: phosphodiesterase (PDE) 5 inhibitors (such as sildenafil, tadalafil, vardenafil) and non-specific phosphodiesterase (PDE) inhibitors (theophylline, dipyridamole), nitrates or NO donors (such as amyl nitrite) in any form a

---

a Pretreatment with the phosphodiesterase (PDE) 5 inhibitor Sildenafil is allowed up to 24 h prior to start of riociguat treatment (Visit 1). Pretreatment with the phosphodiesterase (PDE) 5 inhibitor tadalafil is allowed up to 3 days prior to start of riociguat treatment (Visit 1). Patients are not expected to be withdrawn from treatment with PDE5i for the purpose of entering into this trial. During the period without PDE5i, patients who received treatment with PDE5i are expected to be on stable clinical condition and receiving standard of care treatment with ERA and/or PCAs.

*(Note: The footnote was added by Amendment 6, see Section 17.3.1.4. The footnote text was modified according to Amendment 9, see Section 17.4.1.4)*

- Pretreatment with NO donors (e.g. nitrates) within the last 2 weeks before visit 1. The use of any drug including NO acutely for testing during catheterization is not an exclusion criterion.
- Active state of hemoptysis or pulmonary hemorrhage, including those events managed by bronchial artery embolization or any history of bronchial artery embolization or massive hemoptysis within 3 months prior to screening
- Systolic blood pressure (SBP) more than 5 mmHg lower than the age-, sex- and height-adapted level of the 50th SBP percentile (NHBPEP, 2004) see Table 4–1 and Table 4–2 and appendix 18.5.

**Table 4–1: Age- and sex-adapted SBP (Boys)**

Age (year)	BP percentile	Systolic BP (mmHg)						
		← Percentile of Height →						
		5 TH	10 TH	25 TH	50 TH	75 TH	90 TH	95 TH
6	50 th	91	92	94	96	98	99	100
7	50 th	92	94	95	97	99	100	101
8	50 th	94	95	97	99	100	102	102
9	50 th	95	96	98	100	102	103	104
10	50 th	97	98	100	102	103	105	106
11	50 th	99	100	102	104	105	107	107
12	50 th	101	102	104	106	108	109	110
13	50 th	104	105	106	108	110	111	112
14	50 th	106	107	109	111	113	114	115
15	50 th	109	110	112	113	115	117	117
16	50 th	111	112	114	116	118	119	120
17 *	50 th	114	115	116	118	120	121	122

Note: Age will be rounded down if age is x years and <6 months and rounded up if x years and ≥6 months.

\* Rounding up does not apply for those subjects older than 17 years and 6 months.

**Table 4–2: Age- and sex-adapted SBP (Girls)**

Age (year)	BP percentile	Systolic BP (mmHg)						
		← Percentile of Height →						
		5 TH	10 TH	25 TH	50 TH	75 TH	90 TH	95 th
6	50 th	91	92	93	94	96	97	98
7	50 th	93	93	95	96	97	99	99
8	50 th	95	95	96	98	99	100	101
9	50 th	96	97	98	100	101	102	103
10	50 th	98	99	100	102	103	104	105
11	50 th	100	101	102	103	105	106	107
12	50 th	102	103	104	105	107	108	109
13	50 th	104	105	106	107	109	110	110
14	50 th	106	106	107	109	110	111	112
15	50 th	107	108	109	110	111	113	113
16	50 th	108	108	110	111	112	114	114
17 *	50 th	108	109	110	111	113	114	115

Note: Age will be rounded down if age is x years and <6 months and rounded up if x years and ≥6 months.

\* Rounding up does not apply for those subjects older than 17 years and 6 months.

- History of left-sided heart disease, including valvular disease or heart failure
- Pulmonary hypertension related to conditions other than specified in the inclusion criteria
- WHO functional class IV
- Pulmonary veno-occlusive disease
- Screening aspartate transaminase (AST) and/ or alanine transaminase (ALT) more than 3 times the upper limit of normal (ULN)
- Non-stable disease status, e.g., signs and symptoms of decompensated right heart failure
- Severe bronchial asthma
- Severe restrictive lung disease
- Severe congenital abnormalities of the lung, thorax, and diaphragm
- Clinically relevant hepatic dysfunction (especially Child Pugh C)
- Renal insufficiency (estimated glomerular filtration rate <30 mL/min/1.73m^2 e.g. calculated based on Schwartz formula, for detailed calculation instructions, see [18.6](#))
- Subject with hypersensitivity to the investigational drug or any of the excipients
- Active smoking of tobacco of any type or quantity. Smoking marijuana is also not permitted.
- Subjects with any other condition that is not recommended with riociguat
- Previous assignment to treatment during this study

- Previous (within 30 days) or concomitant participation in another clinical study with investigational medicinal product(s)
- Any condition that, according to treating physician, might jeopardize subject's participation and compliance with procedures indicated in this protocol.
- PH associated with idiopathic interstitial pneumonia (PH-IIP)

*(Note: The section was modified according to Amendment 3, see Sections 17.1.1.16 and 17.1.1.9. The section was modified according to Amendment 5, see Section 17.2.1.6. The Section was modified according to Amendment 6, see Sections 17.3.1.1, 17.3.1.2, 17.3.1.4, and 17.3.1.5. The Section was modified according to Amendment 9, see Sections 17.4.1.4 and 17.4.1.11.)*

#### 4.4 Concomitant medication - amended

Concomitant medication includes either continuation of a treatment started before study entry or addition of a new treatment during the study.

Co-administration of riociguat with the following concomitant medications is not allowed during the study:

- PDE inhibitors: PDE5 inhibitors (such as sildenafil, tadalafil, vardenafil) and nonspecific PDE inhibitors (such as dipyridamole or theophylline) because of increased risk of hypotension
- Nitrates: Nitrates or NO donors (such as amyl nitrite) in any form (e.g. nitrates, molsidomine, sodium nitroprusside) because of increased risk of hypotension

Other concomitant medication considerations:

- Strong multi pathway cytochrome P450 (CYP) and P-glycoprotein 1(P-gp)/breast cancer resistance protein (BCRP) inhibitors: Concomitant use of riociguat with strong multi pathway CYP inhibitors and P-gp/BCRP inhibitors such as azole antimycotics (for example, ketoconazole, itraconazole) or HIV (human immunodeficiency virus) protease inhibitors (such as ritonavir) increase riociguat exposure and may result in hypotension. Consider a starting dose of 0.5 mg TID equivalent when initiating riociguat in subjects on stable doses of strong multi pathway CYP and P-gp/BCRP inhibitors and monitor for signs and symptoms of hypotension. A dose reduction should be considered in subjects who may not tolerate the hypotensive effect of riociguat.
- Strong CYP1A1 inhibitors and strong P-gp inhibitors: The concomitant use of riociguat with strong CYP1A1 (CYP family 1, subfamily A, polypeptide 1) inhibitors, such as the tyrosine kinase inhibitor erlotinib or the reverse-transcriptase inhibitor abacavir, and strong P-gp inhibitors, such as the immunosuppressive agent cyclosporine A, may increase riociguat exposure. In *vitro*, abacavir, rilpivirine, efavirenz, ritonavir, cobicistat and elvitegravir inhibited CYP1A1 and the metabolism of riociguat in the order listed with abacavir as the strongest inhibitor. Concomitant administration of HAART combinations with the drugs listed before led to an increase in riociguat mean AUC of up to about 160%. All these drugs should be used with caution. Blood pressure should be monitored and dose reduction of riociguat considered.

- Strong CYP3A4 inducers: The concomitant use of riociguat with strong CYP3A4 inducers (e.g. phenytoin, carbamazepine, phenobarbitone or St. John's Wort) may lead to decreased riociguat plasma concentration.
- Antacids: Co-administration of the antacid aluminum hydroxide / magnesium hydroxide reduced riociguat mean area under the curve (AUC) by 34% and mean maximum concentration ( $C_{max}$ ) by 56%. Antacids should be taken at least 1 hour after riociguat.
- Omeprazole: Pre- and co-treatment with the proton pump inhibitor omeprazole (40 mg once daily) reduced riociguat mean AUC by 26% and mean  $C_{max}$  by 35%. This is not considered clinically relevant.

Clarithromycin: Co-administration of clarithromycin (500 mg twice daily), classified as strong and selective CYP3A4 inhibitor and also reported to be a weak-to-moderate P-gp inhibitor, moderately increased riociguat mean area under the curve (AUC) by 41% without significant change in  $C_{max}$ . This is not considered clinically relevant.

*(Note: The Section was modified according to the Amendment 3, see Section 17.1.1.16.)*

## 5. Treatment groups and regimens

### 5.1 Method of treatment allocation

Allocation to treatment dose will be done centrally by an interactive voice / web response system (IxRS). All subjects will be allocated to riociguat body-weight adjusted, individual dose titration (IDT).

The investigator will provide the IxRS with study center identification, the subject's date of birth (year) and age, gender, and weight. Further details are contained in the IxRS manual.

#### 5.1.1 Body-weight adjusted individual dose titration regimen - amended

Riociguat must be provided to all patients using an individual dose titration scheme according to a body weight-adjusted dose to achieve a similar exposure as that observed in adults treated for PAH (Figure 5-1). The individual optimal (maintenance) dose is to be determined based on patient's monitoring of systolic blood pressure, well-being and clinical status. For children with <50 kg body weight at baseline, a body weight adjusted dosing will be applied. Children with  $\geq 50$  kg body weight will receive adult doses.

In subjects with a body-weight below 50 kg at baseline, riociguat will be administered as oral suspension TID with or without food. Subjects with a body-weight  $\geq 50$  kg at baseline will receive riociguat as tablet formulation.

The body weight-adjusted riociguat dosing schedule is provided in Table 5-2.

The following tablet strengths will be available: 0.5 mg, 1.0 mg, 1.5 mg, 2.0 mg, and 2.5 mg. An oral suspension formulation of 0.15 mg/mL will also be available.

[figure not shown]
The treatment administration of riociguat oral suspension requires the use of a 5 mL or 10 mL dosing pipette. These dosing pipettes will be calibrated to the required volume of the weight adjusted dose and are manually operated. Each subject will be provided with a new reusable dosing pipette at each drug dispense.

Recommended study medication handling process must be followed.

Educational material for training on the dosing pipette and dose administration for study site staff as well as for the subjects to ensure adequate dosing pipette use and treatment compliance will be distributed.

Subjects with <50 kg body weight will start with body-weight adjusted riociguat dose equivalent to the exposure of 1.0 mg TID in adults. Subjects with  $\geq 50$ kg body weight will start with dose 1.0 mg TID. During the individual titration period, the dose will be up-titrated every 2 weeks ( $\pm 2$  days) at the discretion of the investigator, based on subject's peripheral systolic blood pressure and general tolerability measured at trough before intake of the next higher dose of riociguat. The maximum dose is the dose equivalent to the exposure of 2.5 mg in adults TID. Dose reductions for safety reasons are allowed at any time. The individual dose titration period will not exceed 8 weeks.

Dosing steps and dose equivalents in adults are shown in Figure 5–1.

At each titration visit, the individual dose will be assigned based on the following algorithm where peripheral systolic blood pressure (SBP) will be measured (by oscillometry with the same calibrated oscillometry unit in each center) at trough before intake of the first dose of the day.

*(Note: The description of the dosing of riociguat was clarified according to Amendment 3, see Sections 17.1.1.6, 17.1.1.13, and 17.1.1.16. The Section wording was modified according to Amendment 5, see Section 17.2.1.8. The Section was modified according to Amendment 6, see Section 17.3.1.2.)*

### Dose titration algorithm

- If systolic blood pressure (SBP) is less than 5 mmHg lower than the age-, sex- and height-adapted level of the 50th SBP percentile (NHBPEP, 2004) (see appendix 18.5), increase riociguat dose (+0.5 mg dose-equivalent TID)

- If SBP is  $\geq 5$  mmHg but less than 10 mmHg lower than the age-, sex- and height-adapted level of the 50th blood pressure (BP) percentile, maintain dose of riociguat.
- If SBP is  $\geq 10$  mmHg lower than the age-, sex- and height-adapted level of the 50th BP percentile, reduce riociguat dose (- 0.5 mg dose-equivalent TID)
- If any SBP is  $\geq 5$  mmHg lower than the age-, sex- and height-adapted level of the 50th BP percentile, with clinical symptoms of hypotension such as dizziness or presyncope, stop study treatment; restart after 24 hours with reduced dose - 0.5 mg dose-equivalent TID).

Down-titration of riociguat is possible for safety reasons at any time point. If at any time, the subject has symptoms of hypotension, temporarily stop the medication and restart after 24 hours with a reduced dose (decrease dosage by 0.5 mg dose-equivalent TID).

The sex- and age-adapted height percentile will be determined using standard height charts (see 18.1, Appendix 1). Age-, sex- and height-adapted levels of the 50th BP percentile will be determined according to [Table 4–1](#) and [Table 4–2](#).

If at any time, the subject has symptoms of hypotension, decrease the dosage by 0.5-mg dose equivalent TID.

At the end of the individual titration period (Visit 4), the subjects should have reached their individually adjusted dose (maximum equivalent dose of 2.5 mg riociguat TID). The established individual equivalent dose will then be taken as optimal dose to be administered during the 16-week maintenance period. Dose reductions for safety reasons are allowed in the maintenance phase, but a subsequent re-increase is not possible. During the LTE phase the dose may be up-titrated at the investigator's discretion.

Subjects not tolerating the body-weight adjusted riociguat 0.5 mg TID will be withdrawn from study.

The respective decision (increase, maintain, decrease) will be entered into the IxRS system. The study medication for the next 2-4 weeks will be dispensed to the subjects.

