### **Dose interruptions**

In the case an interruption takes place during the *individual dose titration period* and lasts longer than 3 consecutive days (9 doses missed), it is not allowed to restart the study medication again (respective subjects must be withdrawn from the trial).

In case an interruption takes place after completion of the titration period and lasts longer than 14 consecutive days, it is not allowed to restart the study medication again. In case of shorter interruptions, study medication can be restarted at the discretion of the investigator. Dose interruptions will be communicated to the DMC and/or SC.

*(Note: The dose titration algorithm, dose up-titration in the LTE phase, and wording under dose interruptions were clarified according to Amendment 9, see Sections [17.4.1.10](#), [17.4.1.6](#) and [17.4.1.9](#).)*

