## 6.4 Pharmacokinetics/Pharmacodynamics analyses - amended

Blood samples will be taken for pharmacokinetic and pharmacodynamic measurements from all participants treated with riociguat.

The number of PK blood samples to be taken has been optimized using physiologically based pharmacokinetic (PBPK) modelling predictions in conjunction with clinical trials simulations (CTS) in order to only collect the minimum amount of blood needed for adequate analysis (sparse sampling).

Based on these evaluations the following measures to minimize pain and distress have been included: the number of blood samples in children from 6 to less than 18 years of age for PK analysis must not exceed four, and the minimum amount of blood needed for adequate analysis of each sample is 1.0mL of blood.

The following blood samples will be taken:

**Visit 1:** 2 PK samples will be taken: the first at 0.5 to 1.5 h and the second at 2.5 to 4 h post-dose. Preferred proposal is to have both post-dose samples at the first visit. (To ensure having PK samples in case of drop-outs, both “early post-dose” samples should be collected at the first visit. If this is not feasible, the second post-dose sample can be taken at any visit.)

**Visit 3 and Visit 5:** Trough samples should be collected -1 to 0 hours before the morning dose at both visit 3 and visit 5, which is approx. 5 to 15h after the evening dose.

For all visits in the main study phase, the exact time of three riociguat dosings (current and the previous two doses) and time of PK blood sampling will be documented in the eCRF.

If, for any reason, PK samples are taken outside of the pre-specified time window, the exact time that the sample was taken should be recorded and not the pre-defined time window. If riociguat was temporarily stopped prior to a PK sample collection visit, sampling of blood for PK analysis according to this visit's schedule should be postponed until riociguat treatment has been restarted and sustained for 3 days.

If PK samples are collected at an unscheduled visit or at a visit not foreseeing PK collection, the previous riociguat doses and the time of sampling should be documented like described above. Those samples may be included in the analysis.

Primary PK outcome measure:

Pre- and post-dose blood samples for PK characterization of riociguat and its active metabolite BAY 60-4552 will be collected during the titration and the maintenance phase of the study. For details, see section 7.4.3.

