- If SBP is less than 5 mmHg lower than the age-, sex- and height-adapted level of the 50th SBP percentile [4], increase riociguat dose (+0.5 mg dose-equivalent TID)
- If SBP is ≥ 5 mmHg but less than 10 mmHg lower than the age-, sex- and height-adapted level of the 50th blood pressure (BP) percentile, maintain dose of riociguat.
- If SBP is ≥ 10 mmHg lower than the age-, sex- and height-adapted level of the 50th BP percentile, reduce riociguat dose (- 0.5 mg dose-equivalent TID).
- If any SBP is ≥ 5 mmHg lower than the age-, sex- and height-adapted level of the 50th BP percentile, with clinical symptoms of hypotension such as dizziness or presyncope, stop study treatment; restart after 24 hours with reduced dose (- 0.5 mg dose-equivalent TID).

Down-titration of riociguat is possible for safety reasons at any time point. If at any time, the subject has symptoms of hypotension, temporarily stop the medication and restart after 24 hours with a reduced dose (decrease dosage by 0.5 mg dose-equivalent TID).

At the end of the individual titration phase (Visit 4), the subjects should have reached their individually adjusted dose (maximum equivalent dose of 2.5 mg riociguat TID). The established individual equivalent dose is then taken as optimal dose to be administered during the 16-week maintenance phase. Dose reductions for safety reasons are allowed in the maintenance phase, but a subsequent re-increase is not possible. During the LTE phase the dose may be up-titrated at the investigator’s discretion.

Subjects not tolerating the body-weight adjusted riociguat 0.5 mg TID are to withdraw from study.

During the LTE, subjects receiving stable equivalent dose of 1.0 mg, 1.5 mg, 2.0 mg, or 2.5 mg TID as oral suspension can switch to the tablet formulation at the discretion of the investigator.

4. General Statistical Considerations

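### Protocol 5.1.1 gives two different actions for the same trigger, symptomatic hypotension, and the later sentence drops the 24-hour stop

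*Protocol*

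**What the plan says.** Protocol 5.1.1, under the heading Dose titration algorithm, deals with symptomatic hypotension in three places.

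- The fourth bullet applies when SBP is at least 5 mmHg below the adapted 50th percentile and the child is symptomatic: "with clinical symptoms of hypotension such as dizziness or presyncope, stop study treatment; restart after 24 hours with reduced dose", the reduction being 0.5 mg equivalent TID.
- The paragraph after the bullets drops the SBP condition: "If at any time, the subject has symptoms of hypotension, temporarily stop the medication and restart after 24 hours with a reduced dose", again by 0.5 mg equivalent TID.
- After the paragraph on height percentiles, a sentence opens with the same trigger and gives a shorter action: "If at any time, the subject has symptoms of hypotension, decrease the dosage by 0.5-mg dose equivalent TID".

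SAP 3.2 repeats the fourth bullet and states the unqualified rule once, in its longer form: "temporarily stop the medication and restart after 24 hours with a reduced dose (decrease dosage by 0.5 mg dose-equivalent TID" (the bracket closes after the quoted words). It does not contain the reduction-only sentence.

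Two other provisions depend on whether treatment was stopped. Under Dose interruptions, Protocol 5.1.1 says "Dose interruptions will be communicated to the DMC and/or SC". Protocol 6.4 says of sampling that "If riociguat was temporarily stopped prior to a PK sample collection visit", it "should be postponed until riociguat treatment has been restarted and sustained for 3 days".

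**The concern.** The two unqualified sentences share a trigger word for word. Neither is limited by study phase, SBP level or severity, so they cannot be meant for different situations. One requires a 24-hour stop and the other does not mention it. Protocol 11.1 requires sites to keep strictly to what the protocol specifies, but nothing says which sentence takes precedence.

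Symptomatic hypotension is an adverse event of special interest (Protocol 8.8) and the main hazard that the titration scheme is built to control. Read literally, the later sentence lets a site carry on dosing a symptomatic child at the next lower dose. Sites could also record the same event differently, because Protocol 8.4 treats interruption and dose reduction as separate categories of action taken. The difference then carries through to reporting to the DMC and/or SC and to the timing of trough samples, in a study where pharmacokinetics is part of the primary objective.

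**Working it through.** The plan states no figure to reproduce here. The check is a comparison of texts, followed by short arithmetic on the consequences.

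**The five statements of the rule**

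| Place | Trigger | 24-hour stop? | Dose afterwards |
|---|---|---|---|
| Protocol 5.1.1, fourth bullet | Symptoms and SBP at least 5 mmHg below the 50th percentile | Yes | 0.5 mg equivalent lower |
| Protocol 5.1.1, paragraph after the bullets | Symptoms, at any time | Yes | 0.5 mg equivalent lower |
| Protocol 5.1.1, sentence after the height-percentile paragraph | Symptoms, at any time | **Not mentioned** | 0.5 mg equivalent lower |
| SAP 3.2, fourth bullet | Symptoms and SBP at least 5 mmHg below the 50th percentile | Yes | 0.5 mg equivalent lower |
| SAP 3.2, paragraph after the bullets | Symptoms, at any time | Yes | 0.5 mg equivalent lower |

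Four of the five carry the stop. All five give the same reduction. Stopping for 24 hours and then restarting lower complies with every line. Reducing without stopping complies only with the third row.

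**Doses affected per episode.** Dosing is three times a day, so 24 hours is 3 doses. They are withheld on one reading and given at the reduced level on the other.

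**Pharmacokinetic sampling.** Trough samples are due at Visits 3 and 5. After a stop, the earliest permitted sample is 1 day off plus 3 days back on treatment, which is 4 days after the stop begins, assuming restart at exactly 24 hours. If the stop begins *d* days before the planned visit, the postponement is max(0, 4 − *d*) days:

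- *d* = 1: 4 − 1 = 3 days
- *d* = 2: 4 − 2 = 2 days
- *d* = 3: 4 − 3 = 1 day
- *d* = 4 or more: none

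Under the reduction-only reading the postponement is 0 for every *d*. The flow chart allows ±2 days at Visit 3 and ±4 days at Visit 5. For a visit planned on its target day, the postponed sample misses the Visit 3 window only when 4 − *d* exceeds 2, that is, when *d* is below 2. It stays within the Visit 5 window.

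**What does not change.** The dose level after the episode, the number of dose reductions and the adverse event tables in SAP 6.4.1 are the same on both readings.

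**The case against.** The strongest reply is that the later sentence omits the stop without forbidding it. It repeats the one element common to all five statements, and a site would have to overlook two explicit stop instructions in the same section to act on it alone. That is fair, and it limits how often the literal reading would be followed. It does not cure the defect: a free-standing instruction with the same trigger, placed later, reads as complete.

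A second reply is that the text might intend two tiers: symptoms with low SBP mean stop, and symptoms alone mean reduce. This would give the SBP condition in the fourth bullet some work to do. But the paragraph after the bullets requires the stop with no SBP condition, and SAP 3.2 says the same, so the two-tier reading contradicts both. Deleting the later sentence does leave the fourth bullet as a special case of the general rule. That is redundant but consistent.

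Third, the practical effect is small, and this stands. The doses in question are already reduced, and investigators may act for safety at any time. The DMC sees the event in either case, because it reviews adverse events of special interest (Protocol 6.6.2) and they are in its package (SAP 6.4.1). Only the separate interruption notice differs. Postponement of a trough sample arises only when a stop begins less than 4 days before one of two visits, and Protocol 6.4 provides for recording the actual time of samples taken outside their windows.

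**Conclusion.** The concern holds. The current protocol text gives two actions for one trigger, and the reduction-only sentence disagrees with the other four statements of the rule. The effect is about three TID doses per episode, given at a reduced level instead of being withheld. There may also be a missed interruption notice, and up to 4 days' difference in the timing of a trough sample if the episode falls just before Visit 3 or Visit 5. This assumes a site follows the later sentence alone and that treatment restarts promptly at 24 hours. The documents do not say how often such episodes are expected, so the total across the study cannot be given. No endpoint, sample size, analysis or safety table is affected. It merits correction because it is a child-safety instruction that sites act on directly, and the right wording is already in the documents.

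**What to change.** Delete the later, reduction-only sentence from the dose titration algorithm in Protocol 5.1.1. The 24-hour stop with restart at a dose 0.5 mg equivalent lower is then the only rule, in agreement with the fourth bullet and SAP 3.2. The SAP needs no change.

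The edit is one sentence and calls for no new clinical judgement. Because it is dosing text it belongs in a protocol amendment, which each principal investigator must sign before it takes effect at the site (Protocol 12). It can be bundled with the next amendment, with a short clarification to sites in the meantime.
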